Cerebrolysin as an Early Add-on to Reperfusion Therapy: Risk of Hemorrhagic Transformation after Ischemic Stroke (CEREHETIS). A Prospective, Randomized, Active-Control, Multicenter Pilot Study

Statistical Analysis Plan

Date of issue: 01 December 2020 (study's original report)

Editing:

- 01 May 2023: Added SAP for post hoc analysis (heterogeneous treatment effect analysis)
- 25 April 2024: Added SAP for secondary analysis (survival analysis)

I. Statistical Analysis Plan (Original Study)

1. Introduction

The CEREHETIS trial is a prospective, randomized, multicenter study designed to evaluate the efficacy and safety of Cerebrolysin as an adjunct to reperfusion therapy in patients with acute ischemic stroke (AIS). Hemorrhagic transformation (HT) remains a serious complication of intravenous thrombolysis (IVT) in AIS, contributing significantly to poststroke morbidity and mortality. Cerebrolysin, a neuroprotective agent, has shown promise in preclinical studies for its potential to reduce blood-brain barrier permeability and mitigate neuroinflammation. This study aims to determine whether the addition of Cerebrolysin to standard IVT can reduce the incidence of HT and improve neurological recovery and functional outcomes in stroke patients.

The primary outcome focuses on the rate of any HT and symptomatic HT within 14 days post-intervention, while secondary outcomes include assessments of safety, neurological recovery, and long-term functional status. Advanced imaging analyses, including diffusion-tensor imaging (DTI) and computed tomography (CT) perfusion, will provide further insights into the impact of Cerebrolysin on brain recovery.

2. Objective and Endpoints

- **Primary Objective**: To assess whether Cerebrolysin reduces the incidence of any and symptomatic hemorrhagic transformation (HT) within 14 days in AIS patients undergoing IVT.
- Secondary Objectives:
 - To evaluate neurological recovery using the National Institutes of Health Stroke Scale (NIHSS) at day 1 and day 14.
 - To assess long-term functional outcomes using the modified Rankin Scale (mRS) at day 90.
 - To assess the safety of Cerebrolysin in combination with IVT by evaluating adverse event (AE) rates.
 - To explore changes in advanced imaging parameters, specifically DTI and CT perfusion metrics, as markers of Cerebrolysin's effect on blood-brain barrier integrity and infarct recovery.

3. Trial Design

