The CEREHETIS trial is a prospective, randomized, open-label, multicenter, parallel-group, phase IIIb pilot study with an active control. Patients are randomized in a 1:2 ratio to receive either IVT alone or IVT with Cerebrolysin.

4. Sample Size Calculation

- **Primary Endpoint (HT Rate)**: Based on the assumption that 20% of control group patients will experience HT, with a target odds ratio (OR) of 0.5 in the Cerebrolysin group.
- Significance Level: 0.05
- **Power**: 80%
- Dropout Rate: 10%
- **Design:** 1:2 allocation ratio between the intervention and control groups to optimize power efficiency and minimize required sample size for this pilot study.

5. Randomization and Blinding

- **Randomization**: Simple randomization across centers using Bernoulli variates (probability parameter of 0.333), with sealed opaque envelopes for treatment allocation.
- **Blinding**: Due to the distinct yellow color of Cerebrolysin, treatment blinding was not feasible; however, imaging analyses are blinded.

6. Data Collection and Time Points

Data collection occurs at the following time points:

- Baseline (Day 0): Demographic data, NIHSS, CT, DTI baseline imaging
- Day 1: Follow-up imaging and NIHSS assessment
- Day 7 and Day 14: NIHSS score, follow-up CT, and DTI imaging on day 14
- Day 90: Modified Rankin Scale (mRS) assessment for functional outcome

7. Statistical Analysis

a. Descriptive Statistics

- **Continuous Variables**: Presented as median (M) and interquartile range (IQR) due to non-normal distributions.
- **Categorical Variables**: Presented as percentages and analyzed with χ^2 -tests.

b. Comparative Analysis

- Primary Analysis (HT Rates):
 - Comparison of HT Rates: Logistic regression will compare the rates of any and symptomatic HT between the Cerebrolysin and control groups. Odds ratios (OR) with 95% confidence intervals (CI) will be reported.
 - Adjustment for Confounders: Age, NIHSS, ASPECTS score, and baseline variables such as history of hypertension and previous stroke will be included in multivariate models to control for potential confounding.
- Secondary Analysis:
 - **Neurological Recovery (NIHSS)**: The Mann–Whitney U test will compare NIHSS scores between groups at day 1 and day 14.
 - **Functional Outcome (mRS)**: The mRS scores on day 90 will be assessed using a χ^2 -test for favorable outcomes (mRS ≤ 2). Additionally, a shift analysis will be conducted to evaluate distributional differences in mRS scores between groups.

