c. Advanced Imaging Analysis (Exploratory)

- Evaluate DTI and CT perfusion parameters in middle cerebral artery (MCA) stroke patients, focusing on markers such as fractional anisotropy, axial, radial, and mean diffusivity, and permeability–surface area product (PS).
- Statistical Methods:
 - **Group Comparisons**: The Mann–Whitney U test will be used to compare continuous imaging metrics between the Cerebrolysin and control groups at each time point (day 1 and day 14).
 - Laterality Index Analysis: Calculate the laterality index to assess asymmetry in imaging metrics between the affected and contralateral sides, with paired t-tests or Wilcoxon signed-rank tests for within-group comparisons from day 1 to day 14.

• **Correlation Analysis**: Spearman's rank correlation coefficient will evaluate associations between imaging metrics (e.g., DTI metrics and PS values) and clinical outcomes, such as NIHSS scores and HT incidence.

8. Safety Analysis

• Adverse Events (AEs): Safety will be assessed by tracking and comparing the incidence of AEs in each group, with specific attention to known Cerebrolysin side effects such as mild agitation and hypotension. Proportions will be compared using χ^2 -tests or Fisher's exact test, as appropriate.

9. Software and Statistical Significance

- Software: STATA v.14.2 and IBM SPSS v.26.
- **Significance Level**: α = 0.05 for primary and secondary endpoints, with multiple hypothesis correction for primary outcomes using Romano-Wolf adjustment.

This Statistical Analysis Plan (SAP) provides a detailed framework for assessing the impact of Cerebrolysin on hemorrhagic transformation, neurological recovery, functional outcomes, and safety in MCA stroke patients undergoing IVT. The exploratory imaging analysis aims to substantiate Cerebrolysin's neuroprotective role by examining advanced imaging biomarkers of blood-brain barrier stability and infarct recovery. This SAP is essential for ensuring that the study findings are robust, reproducible, and clinically meaningful.

II. Statistical Analysis Plan for Post Hoc Analysis of the CEREHETIS Trial (Heterogeneous Treatment Effect Analysis)

1. Introduction

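### In the exploratory imaging analysis, the laterality index is assigned only a within-arm day-1-to-day-14 test, which measures evolution over time and not a Cerebrolysin effect, and the scheduled day-0 DTI enters no timed analysis

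*SAP*

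**What the plan says.** All references are to Part I of the SAP.

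- **Aim.** Section 2 lists among the secondary objectives "To explore changes in advanced imaging parameters, specifically DTI and CT perfusion metrics, as markers of Cerebrolysin's effect". The closing paragraph after Section 9 says: "The exploratory imaging analysis aims to substantiate Cerebrolysin's neuroprotective role".
- **Laterality index.** Section 7c has the index calculated to describe asymmetry between the affected and the opposite side, "with paired t-tests or Wilcoxon signed-rank tests for within-group comparisons from day 1 to day 14".
- **Between-arm imaging test.** The bullet above it in 7c uses the Mann–Whitney U test to "compare continuous imaging metrics between the Cerebrolysin and control groups at each time point (day 1 and day 14"). It does not mention the laterality index.
- **Schedule.** Section 6 lists "Baseline (Day 0): Demographic data, NIHSS, CT, DTI baseline imaging", then "Day 1: Follow-up imaging and NIHSS assessment", then for days 7 and 14 "NIHSS score, follow-up CT, and DTI imaging on day 14". The day-1 entry names no imaging modality.
- **Status.** Section 7c is labelled exploratory.

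**The concern.** The imaging objective is about change as a marker of what Cerebrolysin does. The only analysis of change in 7c is a paired test inside each arm. That test asks whether patients in one arm differ between day 1 and day 14. The answer mixes natural evolution of the infarct with any treatment effect and makes no use of the randomized comparison.

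Two separate within-arm p-values are also easily misread. If one arm is significant and the other is not, a reader tends to see a treatment effect, although no difference between arms has been tested. Unequal allocation adds to this, because for the same true change the larger arm has more power.

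There is a second, smaller point. The schedule provides a day-0 DTI, which could serve as a baseline covariate or as the start of the change. Both timed analyses in 7c use day 1 and day 14 only. Either a scheduled baseline scan goes unused, or the first DTI is really the day-1 scan and Section 6 labels it differently. Day 1 follows the baseline visit, so change measured from day 1 may already have lost part of an early effect.

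**Working it through.** **Step 1: does any listed analysis compare change between arms?**

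| Analysis in 7c | Names the index? | Between arms? | Change over time? | Uses day-0 DTI? |
|---|---|---|---|---|
| Mann–Whitney U | No, but may cover it | Yes | No, each visit separately | No |
| Laterality index, paired tests | Yes | No | Yes, day 1 to day 14 | No |
| Spearman correlation | No | No | No time point given | Not stated |

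No row combines a between-arm comparison with change or with adjustment for an earlier scan. The day-0 point applies to DTI only, because Section 6 names no visit for CT perfusion.

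**Step 2: how often could paired tests mislead?** The SAP gives no sample size, standard deviation or effect size for the imaging analysis, so it has no figure to reproduce. What follows is an illustration.

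Inputs:
- Allocation 1:2, from Section 3. Arms of size n and 2n are assumed.
- Alpha 0.05, from Section 9. Two-sided is assumed, as the SAP does not say.
- The same true standardized within-patient change d in both arms, so no treatment effect. The values of n and d are assumed.

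Formulas:
- Power of a paired t-test with n pairs = P(T > c) + P(T < −c). T is noncentral t with n − 1 degrees of freedom and noncentrality d√n, and c is the 97.5% point of central t.
- With power a in the smaller arm and b in the larger, P(exactly one significant) = a(1 − b) + b(1 − a). The part in which only the larger arm is significant is b(1 − a).

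Example, 20 and 40 patients, d = 0.5:
- Noncentralities: 0.5 × √20 = 2.236 and 0.5 × √40 = 3.162.
- Powers: a = 0.565, b = 0.869.
- Smaller arm only: 0.565 × 0.131 = 0.074.
- Larger arm only: 0.869 × 0.435 = 0.378.
- Exactly one arm: 0.074 + 0.378 = 0.452, or 45%.

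Wider grid:

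| Arms | d | a | b | Exactly one | Larger arm only |
|---|---|---|---|---|---|
| 15/30 | 0.2 | 0.112 | 0.185 | 0.255 | 0.165 |
| 15/30 | 0.3 | 0.192 | 0.355 | 0.411 | 0.287 |
| 15/30 | 0.5 | 0.438 | 0.754 | 0.532 | 0.424 |
| 30/60 | 0.2 | 0.185 | 0.332 | 0.394 | 0.270 |
| 30/60 | 0.3 | 0.355 | 0.628 | 0.537 | 0.405 |
| 30/60 | 0.5 | 0.754 | 0.968 | 0.262 | 0.238 |
| 60/120 | 0.2 | 0.332 | 0.584 | 0.528 | 0.391 |
| 60/120 | 0.3 | 0.628 | 0.903 | 0.397 | 0.336 |
| 60/120 | 0.5 | 0.968 | 1.000 | 0.032 | 0.032 |
| 100/200 | 0.2 | 0.508 | 0.804 | 0.495 | 0.395 |
| 100/200 | 0.3 | 0.844 | 0.988 | 0.164 | 0.154 |
| 100/200 | 0.5 | 0.999 | 1.000 | 0.001 | 0.001 |

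With d = 0 the figure is 2 × 0.05 × 0.95 = 0.095 at every size. For d > 0 the range is about 0% to 54%. It is near zero only where both arms are almost sure to be significant. In every row above, the larger arm accounts for most of the discordant trials.

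**The case against.** The case on the other side is substantial.

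- **A between-arm test is planned.** A laterality index is a continuous imaging metric, so the Mann–Whitney bullet may include it. An unadjusted day-14 comparison is valid under randomization, and adjusting for an earlier scan mainly adds precision. This stands. A reader might infer that the imaging is not compared between arms at all, and the text does not support that. What remains is that the bullet neither names the index nor compares change.
- **No misleading rule is written down.** A reader might infer that the SAP will take significance in one arm only as evidence of effect. No section says so, and within-arm change is a legitimate description beside a between-arm test. This also stands. The risk comes from setting such tests next to an aim of substantiating a neuroprotective role.
- **The direction is not settled.** Section 3 makes Cerebrolysin the larger arm, while Section 4 words the ratio the other way round. The claim that the artefact favours Cerebrolysin therefore cannot be taken from the SAP without reconciling those two sections.
- **Sections 6 and 7c need not contradict each other.** The day-1 imaging in Section 6 has no stated modality, so a day-1 DTI is not excluded, and 7c never calls day 1 a baseline. The timing is ambiguous. Nor does the SAP give a dosing schedule, so it does not establish that treatment had begun before the day-1 scan.
- **The analysis is exploratory.** This limits the weight of the point but does not make the paired test an estimate of treatment effect.

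**Conclusion.** The point holds in a limited form. The only test named for the laterality index, and the only analysis of change in 7c, is within-arm and does not estimate a Cerebrolysin effect. The day-0 DTI enters no timed analysis, and the visit of the first DTI is unclear.

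This part of the verdict rests on the text alone. The size of the possible misreading, about 0% to 54% of trials with exactly one significant arm under identical change, depends on assumed imaging subsets and effect sizes, independent arms, two-sided testing and paired t-tests. It should be read as an illustration. The consequence is confined to the exploratory imaging; the correction is a nearly free improvement.

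**What to change.** 1. In 7c, make the between-arm comparison of the day-14 laterality index, adjusted for the day-0 DTI value, the analysis of treatment effect. Report the adjusted difference with its 95% CI. Use ANCOVA, or a rank-based or robust equivalent, since 7a describes the continuous data as non-normal.
2. Keep the within-arm paired tests, labelled as descriptive and not to be contrasted between arms.
3. Use one reference visit for all patients. Taking day 0 where available and day 1 otherwise would mix covariates measured before and after randomization.
4. If day 1 proves to be the first DTI, report the between-arm day-14 difference without adjustment for it as the main estimate. Label any day-1-adjusted result as conditional on a post-randomization scan.
5. Reconcile Section 6 and 7c on the day of the first DTI, and say whether the Mann–Whitney bullet covers the laterality index.

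The cost is SAP wording and one model per metric. No new scans are needed.

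### The only inference planned for adverse events is a significance test, so a non-significant result would say little about how large an excess of an uncommon AE has been ruled out

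*SAP*

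**What the plan says.** Section I.2 lists safety among the secondary objectives: "To assess the safety of Cerebrolysin in combination with IVT by evaluating adverse event (AE) rates". Section I.8 sets out the analysis. It says "Safety will be assessed by tracking and comparing the incidence of AEs in each group", with particular attention to mild agitation and hypotension, and then: "Proportions will be compared using χ^2 -tests or Fisher's exact test, as appropriate". It names no risk difference, risk ratio, confidence interval or bound.

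The HT outcomes are treated differently. Section I.7b requires an effect measure with an interval: "Odds ratios (OR) with 95% confidence intervals (CI) will be reported".

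Section I.4 gives the inputs to the sample size (20% control HT rate, odds ratio 0.5, significance level 0.05, power 80%, dropout 10%, 1:2 allocation) but no resulting N. No expected AE rate appears anywhere in the SAP.

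**The concern.** A test of equal proportions answers whether a difference has been shown. A safety objective asks something else: how large an excess on Cerebrolysin remains compatible with the data. A p-value does not answer that, and it is least informative for uncommon events in a trial sized for a 20% event rate.

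At stake is the wording of the safety conclusion. If a key AE yields p > 0.05, the plan prescribes no quantity that tells the reader whether an excess of one, three or six percentage points has been excluded. For the less common AEs, a non-significant result would be frequent even if the true rate had doubled.

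**Working it through.** **Inputs from the SAP (section I.4).** Control HT rate: "20% of control group patients will experience HT". Effect: "with a target odds ratio (OR) of 0.5 in the Cerebrolysin group". Power is 80% and dropout 10%. The significance level is 0.05 with no sidedness given; two-sided is taken here. Section I.3 reads as control:Cerebrolysin = 1:2, while section I.4 can be read as Cerebrolysin:control = 1:2, so both are carried through.

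**Assumed inputs.** Control AE rates of 2%, 3%, 5% and 10%, each doubled on Cerebrolysin.

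**Step 1: implied evaluable N.** The SAP states no N to reproduce, so it has to be derived.

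- Control odds are 0.20/0.80 = 0.25. Halved, they are 0.125, so p1 = 0.125/1.125 = 0.111.
- With k = Cerebrolysin/control and p̄ = (p0 + k·p1)/(1 + k), the control arm needs n = [1.96·√((1 + 1/k)·p̄(1 − p̄)) + 0.842·√(p0(1 − p0) + p1(1 − p1)/k)]² / (p0 − p1)².
- k = 2: p̄ = 0.141, n = 188.3, giving 189 control + 378 Cerebrolysin = 567 (unrounded total 565). With dropout: 567/0.9 = 630.
- k = 0.5: p̄ = 0.170, n = 400.8, giving 401 control + 201 Cerebrolysin = 602 (unrounded total 601). With dropout: 602/0.9 = 669.

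**Step 2: chance of missing a doubled AE rate.** All pairs of binomial counts were enumerated. The rule was Pearson chi-square, or Fisher's exact test if any expected count was below 5, two-sided at 0.05.

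| Control vs Cerebrolysin rate | 189 / 378 (2/3 treated) | 401 / 201 (1/3 treated) |
|---|---|---|
| 2% vs 4% | 79% | 69% |
| 3% vs 6% | 67% | 57% |
| 5% vs 10% | 46% | 37% |
| 10% vs 20% | 12% | 9% |

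Using Fisher's test throughout raises these slightly (2% vs 4%: 81% and 73%; 5% vs 10%: 47% and 41%).

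**Step 3: sensitivity to N.** If the dropout-inflated numbers are all evaluable for AEs (210/420 or 446/224 after rounding), the miss rates under the same rule are 76% and 67% at 2% vs 4%, and 41% and 33% at 5% vs 10%. For 80% power to detect a doubling, the total N would have to be about 2,450-2,670 at 2%, or 940-1,020 at 5%.

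**Step 4: what an interval would show.** Take N = 600 and 5% observed in both arms. The Newcombe upper limit for the excess is √[(u_T − 0.05)² + (0.05 − l_C)²], where u_T is the upper Wilson limit on Cerebrolysin and l_C the lower Wilson limit on control.

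- 400 treated, 200 control: √[(0.0760 − 0.05)² + (0.05 − 0.0274)²] = 0.034, or 3.4 percentage points.
- 200 treated, 400 control: √[(0.0896 − 0.05)² + (0.05 − 0.0326)²] = 0.043, or 4.3 percentage points.

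These limits hold for observed rates that happen to be equal. When the true rate is 5% in both arms, the upper limit exceeds 5 points, and so fails to exclude a doubling, in about 18% (2/3 treated) to 37% (1/3 treated) of trials.

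**The case against.** The strongest reply is that nothing in the SAP is wrong as stated. Comparing AE proportions by chi-square or Fisher's test is common, low power for uncommon AEs affects most trials sized for efficacy, and this one calls itself a pilot. The SAP makes no equivalence or non-inferiority claim, so no margin is owed. Incidence is tracked per group, so a reader could compute a risk difference and interval from the table. HT, itself a serious harm of thrombolysis, does get an interval.

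Much of this stands, and it rules out three stronger readings:

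- A reader might infer that the plan equates a non-significant test with safety. No sentence in the SAP says so; the test-only plan merely leaves that reading open.
- A reader might infer that the trial would usually miss any doubled AE. The table shows otherwise: a doubling from 5% is detected more often than not, and one from 10% about 90% of the time. Missing it most of the time applies to the 2-3% rates.
- A reader might infer that an interval cures the problem. It does not, as step 4 shows.

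What does not stand is that nothing needs changing. The choice of AE inference belongs in a SAP, and section I.8 makes that choice. That readers could derive the missing quantity themselves is no reason for the plan not to require it when safety is a stated objective.

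**Conclusion.** The point holds as a weakness in the chosen analysis: section I.8 fixes a test as the sole inference for a stated objective that calls for an estimate with a bound. For AEs of about 2-5%, a non-significant result would say little about the excess ruled out, with a doubling missed about 37-79% of the time at the implied evaluable N; for AEs near 10% the concern is small.

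These figures rest on assumed AE rates, two-sided testing, arm sizes fixed at the nominal ratio, and an N derived from section I.4 rather than stated there. The conclusion is the same under both readings of the allocation. The primary analysis is unaffected. The change is worth making because it is cheap and makes the safety conclusion quantitative.

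**What to change.** In section I.8, for each key AE class (any AE, serious AE, agitation, hypotension), report the number and percentage per arm and the risk difference (Cerebrolysin minus control) with a 95% confidence interval by the Newcombe or Miettinen-Nurminen method. Word the safety conclusion by the upper limit, that is, by the excess in percentage points that the data exclude. State that p > 0.05 will not be taken as evidence of safety, and keep the chi-square or Fisher p-values as descriptive.

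The cost is a few sentences in the SAP and one extra column in the AE tables. The counts are already planned, so no new data are needed. The downside is a less favourable safety statement wherever the upper limit is wide.

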3.1 HT Risk Stratification

- Scores Used:
 - DRAGON: Combines clinical and imaging features such as the hyperdense MCA sign, pre-stroke mRS, age, glucose levels, onset-to-treatment time, and NIHSS score.

- **SEDAN**: Uses predictors such as blood sugar, ASPECTS score, hyperdense MCA sign, age, and NIHSS score to predict symptomatic HT.
- **HTI**: Predicts HT risk using ASPECTS, NIHSS, hyperdense MCA sign, and atrial fibrillation presence, specifically tailored to MCA strokes.

• Model Selection:

 A regression analysis will be performed to evaluate each scoring tool's effectiveness in predicting HT and FFO. The score with the best predictive performance (expected to be HTI) will be selected as the primary risk stratification tool.

3.2 Descriptive and Comparative Analysis

• Descriptive Statistics:

- Continuous variables will be presented as medians with interquartile ranges (IQR) and compared using the Mann–Whitney U test.
- $\circ~$ Categorical variables will be presented as percentages and compared using Pearson's χ^2 -test.
- Logistic Regression for Score-Adjusted Treatment Effects:
 - Logistic regression models will assess the impact of Cerebrolysin on symptomatic HT and FFO, adjusting for each risk score (HTI, DRAGON, and SEDAN) individually and in combination.
 - $\circ~$ Odds ratios (ORs) with 95% confidence intervals (CI) will be calculated.

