3.3 Conditional Marginal Effects and Propensity Score Matching

- Conditional Marginal Effects:
 - For each HT risk level, conditional marginal effects will be estimated to quantify the Cerebrolysin effect on the likelihood of symptomatic HT and achieving FFO.

• Propensity Score Matching:

- Propensity scores will be calculated for each patient based on baseline covariates, such as age, NIHSS, and comorbidities, to balance baseline differences between treated and untreated patients.
- Treatment effects will be estimated for matched cohorts using:
 - Average Treatment Effect (ATE): Overall effect across the population.
 - Average Treatment Effect on the Treated (ATT) and Average Treatment Effect on the Untreated (ATC).

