3.6 Meta-Analysis for Subgroup Heterogeneity

• Meta-analytic Techniques:

- Subgroups defined by HT risk scores (e.g., low, moderate, high HTI scores) will be treated as individual "studies" in a meta-analysis framework.
- Effect Size and Heterogeneity Assessment:
 - Fixed-effects Mantel–Haenszel models will assess binary outcomes, while random-effects models will evaluate heterogeneity using I² and H² statistics.
 - Small-study effects will be tested with the Egger test.
- Visualization: A forest plot will display effect sizes across subgroups.

4. Software and Statistical Significance

- Software: Stata v.14.2 and Stata v.17.0.
- **Significance Level**: α = 0.05 for all primary and secondary outcomes, with corrections for multiple comparisons using the Romano-Wolf adjustment.

5. Interpretation and Reporting

- Heterogeneity and Interpretation of HTEs:
 - Results will highlight subgroups where Cerebrolysin significantly reduces HT or improves functional outcomes. Any significant HTE findings will guide further investigation and inform potential stratification for future clinical recommendations.
- Limitations:
 - Post hoc analyses bear an inherent risk of finding spurious associations. To address this, all models and outcomes will be rigorously tested and reported regardless of significance. Additionally, findings will be discussed within the context of generalizability and the need for prespecified subgroup analyses in future trials.

This SAP for the post hoc analysis of the CEREHETIS trial outlines a robust, stratified approach to identify subgroups with potential benefits from Cerebrolysin. Advanced statistical methods for matching, smoothing, and meta-analysis will help address treatment heterogeneity, contributing valuable insights into personalized treatment strategies in ischemic stroke.

III. Statistical Analysis Plan for Secondary Data Analysis of the CEREHETIS Trial (Survival Analysis)

1. Introduction

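### Part II makes heterogeneity of effect by HT risk its primary objective but names no treatment-by-risk interaction test and no effect scale, so heterogeneity may be inferred where the odds ratio is constant

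*SAP*

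**What the plan says.** All references are to the SAP, Part II, unless stated.

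- **Section 2** sets HTE by HT risk level as the primary objective. The primary endpoints are any HT, symptomatic HT and the day-90 mRS, with favorable functional outcome (FFO) defined from it. Subgroup-specific effects are secondary endpoints.
- **Section 3.1** selects one risk score by predictive performance and expects it to be HTI.
- **Section 3.2**: "Logistic regression models will assess the impact of Cerebrolysin on symptomatic HT and FFO, adjusting for each risk score (HTI, DRAGON, and SEDAN) individually". The scores are also to be entered jointly. Any HT is not named.
- **Section 3.3**: "For each HT risk level, conditional marginal effects will be estimated to quantify the Cerebrolysin effect on the likelihood". The outcomes listed are symptomatic HT and FFO. The underlying model is not named, and any HT is again absent.
- **Section 3.4** smooths matched treatment effects over risk and gives bootstrap 95% intervals. No test against a constant effect and no effect scale are given.
- **Section 3.6** treats risk strata as studies, with low, moderate and high HTI as the example, and uses I-squared and H-squared. It adds: "Small-study effects will be tested with the Egger test".
- **Section 4** applies a Romano-Wolf correction.
- **Section 5**: "Results will highlight subgroups where Cerebrolysin significantly reduces HT or improves functional outcomes". It also promises reporting whatever the significance and warns of spurious post hoc findings.

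**The concern.** A claim that the effect differs by risk needs a comparison of effects between risk levels, on a stated scale. Two features of the plan can show variation without one.

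First, a logit with treatment and score but no product term has a single OR. Turned into probabilities, that OR gives larger absolute effects at higher baseline risk, up to 50%. The variation comes from the link function and is not evidence that the OR changes.

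Second, significance within a subgroup depends on its size and event rate. One stratum can reach 0.05 and its neighbor miss it with the same OR in both.

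At stake is the conclusion of Part II, since Section 5 intends HTE findings to feed into stratification in future clinical recommendations.

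**Working it through.** The SAP states no sample size, stratum size or stratum risk, so there is no figure to reproduce. The steps below use its planning assumptions and mark what is assumed.

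**Inputs from Part I, Section 4.** "Based on the assumption that 20% of control group patients will experience HT", and "target odds ratio (OR) of 0.5 in the Cerebrolysin group"; alpha 0.05 (taken as two-sided), power 80%.

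**Step 1. Absolute effect under a constant OR.** With control risk p, the treated odds are 0.5 x p/(1 - p), and the treated risk is odds/(1 + odds).

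| Control risk | Treated risk | Risk difference (points) |
|---|---|---|
| 2% | 1.0% | -1.0 |
| 20% | 11.1% | -8.9 |
| 50% | 33.3% | -16.7 |

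The OR is the same in every row.

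**Step 2. Implied size.** For 20% against 11.1%, without continuity correction or dropout, with k Cerebrolysin patients per control and pbar = (p1 + k p2)/(1 + k):

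n(control) = [1.96 sqrt(pbar(1 - pbar)(1 + 1/k)) + 0.84 sqrt(p1(1 - p1) + p2(1 - p2)/k)]^2 / (p1 - p2)^2.

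Part I can be read as k = 2 (Section 3) or k = 1/2 (Section 4). These give 189 + 378 = 567 and 401 + 201 = 602. N = 300 was added as an assumed smaller case.

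**Step 3. Significance by stratum under a constant OR of 0.5, any HT.** Three strata are assumed, in two patterns:

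- Pattern A: shares 50/30/20%, control risks 8/22/45% (average 0.5 x 8 + 0.3 x 22 + 0.2 x 45 = 19.6%).
- Pattern B: equal thirds, control risks 5/18/37% (average 20%).

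Each stratum is tested for benefit with a Pearson test at two-sided 0.05, over 40,000 simulated trials. Discordant means that one or two of the three strata are significant. Bonferroni over three strata stands in for Romano-Wolf.

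| N (share on Cerebrolysin) | Pattern | Discordant, unadjusted | Discordant, Bonferroni | All three significant, unadjusted | Cochran Q on log OR, P < 0.05 |
|---|---|---|---|---|---|
| 567 (2/3) | A | 68.6% | 50.7% | 4.1% | 3.8% |
| 567 (2/3) | B | 72.8% | 54.6% | 2.9% | 2.5% |
| 602 (1/3) | A | 65.7% | 42.4% | 2.8% | 3.5% |
| 602 (1/3) | B | 70.2% | 47.6% | 1.3% | 3.1% |
| 300 (1/3) | A | 41.9% | 19.3% | 0.4% | 2.4% |
| 300 (1/3) | B | 40.5% | 20.5% | 0.0% | 2.0% |

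Hand check of the first row: power by stratum is 27.5%, 37.2% and 39.6%. P(none) = 0.725 x 0.628 x 0.604 = 0.275 and P(all) = 0.275 x 0.372 x 0.396 = 0.041, so P(discordant) = 1 - 0.275 - 0.041 = 0.684, in line with the simulation. A repeat with another seed gave 40 to 72% unadjusted.

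For symptomatic HT (assumed control risks 1/4/12%, N = 400), discordance was 10 to 30%.

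**Step 4. Methods that compare strata.** Under the same constant OR, a likelihood-ratio test of treatment by risk level rejected in 6.3% of 1,500 runs at N = 400 (Monte Carlo standard error about 0.6 points). Q on the log OR rejected in 2 to 4%. Q on the risk difference rejected in 15 to 35%, because risk differences do vary. The answer therefore depends on the scale, which the plan leaves open.

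**Step 5. Section 3.6 with three strata.** Under homogeneity Q is about chi-square with 2 df, and I-squared = 1 - 2/Q. I-squared above 25% means Q > 2.67, with probability exp(-1.33) = 26%. Above 50% means Q > 4, with probability exp(-2) = 14%. Egger on three points leaves 1 df, with critical t = 12.7.

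**The case against.** The best defense is Section 3.4, the method actually labelled as the HTE analysis. It lets the effect vary with risk and gives intervals, so it would be wrong to infer that every model in Part II forces a constant effect. That stands. But a curve with pointwise intervals is not a test against constancy. If the smoothed quantity is a matched difference in a binary outcome, it lies on the probability scale, where a constant OR also produces a slope.

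Section 3.2 is headed as a score-adjusted effect, for which a main-effects model is ordinary, and 3.3 does not say that it uses that model. The fair statement is that no product term is named. Step 1 applies only if none is fitted.

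A reader might also infer that I-squared and Egger manufacture HTE. The documents do not support this. I-squared is a function of Q, which is not inflated on the OR scale. Its weaknesses are imprecision with few strata and the lack of a stated P value, interval or cut-off. The SAP assigns Egger to small-study effects. On a few risk strata it is uninformative, and three strata is itself only an example.

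Romano-Wolf lowers the discordance, as Step 3 shows. It controls false rejection of no effect and does not test equality of effects. Highlighting a significant subgroup is also not, in words, a claim that subgroups differ. With HTE as the objective, however, it is the only reporting rule given.

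Finally, absolute effects that vary under a constant OR are genuine and may matter for stratification. That is a reason to report them, labelled by scale. The post hoc caveats in Section 5 are proper but supply no test.

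**Conclusion.** The point holds as a gap in the inference rule: Part II specifies no treatment-by-risk interaction test and no effect scale for its primary objective. Under a constant OR of 0.5, reading HTE from significance within strata would mislead for any HT in about 40 to 73% of trials unadjusted, or 19 to 55% with the Bonferroni stand-in. These figures rest on assumed N (300 to 602), three strata, and assumed stratum shares and risks. For symptomatic HT the unadjusted figure is lower, at 10 to 30%.

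A reader might go further and say that HTE will be reported even when the OR is constant. That is not supported. Variation is certain only for absolute effects, where it is real. On the significance route a false reading is likely, not inevitable.

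Leaving any HT out of 3.2 and 3.3 is a plain inconsistency with Section 2. Severity: should be fixed.

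**What to change.** 1. **Section 3.2.** For any HT, symptomatic HT and FFO, fit treatment, the score selected under 3.1 (expected to be HTI; ordered or continuous) and treatment x score. Make the 1-df likelihood-ratio test of the product term on the log-odds scale, with estimate and 95% CI, the basis for any claim that effects differ.
2. **Section 3.3.** Compute marginal effects from that model, include any HT, and report absolute effects separately as scale-dependent.
3. **Section 3.4.** State the scale of the smoothed effect, and that the curve is descriptive unless a test of constancy is added.
4. **Section 3.6.** Report the Q-test P value and a CI for I-squared. Delete Egger.
5. **Section 5.** Reword so that differences between subgroups are not inferred from significance within them.

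The cost is SAP wording and minor programming. The downside is low power: with true ORs of 1, 0.5 and 0.25 across three strata and N = 400, Q has only about 29% power. Fewer subgroup claims will survive, and a non-significant interaction must not be read as proof of a constant effect.
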